10.1.1.1 Sample Size Determination

A maximum of 29 patients with HMP IDH-mutant gliomas, and a maximum of 30 patients with NHMP IDH-mutant gliomas will be enrolled in this phase II trials. Under the design described previously and given the type I error rate of 0.05, we have 80% power to reject the null hypothesis PFS6 = 0.1 for the HMP cohort given the alternative hypothesis PFS6 = 0.3; and 80% power to reject the null hypothesis PFS6 = 0.19 for the NHMP cohort given the alternative hypothesis PFS6 = 0.39.

Up to 59 study patients who undergo at least 1 cycle (2 infusions of nivolumab) is required. As we take into account approximately 20% of screen failures/non-evaluable patients, the overall accrual ceiling is 70 study patients.

10.2 POPULATIONS FOR ANALYSES

10.2.1 Evaluable for toxicity:

All patients will be evaluable for toxicity from the time of their first treatment with nivolumab.

10.2.2 Evaluable for objective response:

Only those patients who have measurable disease present at baseline, have received at least one cycle of therapy, and have had their disease re-evaluated will be considered evaluable for response. These patients will have their response classified according to the definitions stated below. (Note: Patients who exhibit objective disease progression prior to the end of cycle 1 will also be considered evaluable.)

10.2.3 Evaluable Non-Target Disease Response:

Patients who have lesions present at baseline that are evaluable but do not meet the definitions of measurable disease, have received at least one cycle of therapy, and have had their disease re-evaluated will be considered evaluable for non-target disease. The response assessment is based on the presence, absence, or unequivocal progression of the lesions.

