therapy. The primary outcome measure was overall survival (OS), and the secondary outcome included overall survival rate, progression-free survival (PFS), and objective response rate (ORR). The result was presented in May 2017. At the time of final analysis, 369 pts were randomized, where 182 received nivolumab and 165 received bevacizumab. At baseline, 40% patients received nivolumab and 43% of patients received bevacizumab required corticosteroids. The OS was 9.8 months with nivolumab and 10.0 months with bevacizumab, and the 12-mo OS rate was 42% in both arms. PFS medians were 1.5 months (nivolumab) and 3.5 months (bevacizumab). Among evaluable patients treated with nivolumab (n = 153) or bevacizumab (n = 156), ORRs were 8% (nivolumab) and 23% (bevacizumab); duration of response medians was 11.1 months (nivolumab) and 5.3 months (bevacizumab). Treatment-related AEs (TRAEs) occurred in 57% (nivolumab) and 58% (bevacizumab) of patients; the most common TRAEs ($\geq 10\%$ of patients in either arm; nivolumab vs bevacizumab) were fatigue (21% vs 14%) and hypertension (1% vs 22%). Grade 3–4 TRAEs were reported in 18% (nivolumab) and 15% (bevacizumab) of patients. Serious AEs (all causality) were reported in 46% (nivolumab) and 35% (bevacizumab) of patients; seizure (8% vs 6%) and malignant neoplasm progression (11% vs 7%) were the only serious AEs reported in $\geq 5\%$ of patients in either arm. AEs leading to discontinuation occurred in 10% (nivolumab) and 15% (bevacizumab) of patients. Unfortunately, the study did not meet its primary endpoint of improved overall survival over bevacizumab monotherapy. The ORR was lower in the nivolumab arm than the bevacizumab arm. However, the response with nivolumab was more durable. The safety profile of nivolumab was very consistent with what has been observed in other tumor types. [40]

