3 STUDY IMPLEMENTATION

3.1 STUDY DESIGN

This is a phase II study to evaluate the efficacy of treatment with nivolumab in glioma patients with or without HMP.

The study will be conducted in 2 stages.

During stage 1 of the study, 10 patients with HMP and 15 patients with NHMP will be accrued simultaneously into Cohorts 1 (HMP) and 2 (NHMP).

If 9 or more patients with HMP (Cohort 1) progress by 6 months, the Cohort 1 will be terminated early; otherwise, additional 19 patients will be accrued in stage II, resulting in a total sample size of 29.

If 3 or more patients with NHMP (Cohort 2) are progression-free at 6 months, the Cohort 2 will be moved to stage II and additional 15 patients will be accrued, resulting in a total sample size of 30.

All patients will be treated with nivolumab at a flat dose of 240 mg intravenously every 2 weeks (+/- 3 days) for cycles 1 through 2, then at a flat dose of 480 mg every 4 weeks for cycles 3-16. Treatment will be discontinued after 20 treatments given within 64 weeks.

One cycle is 4 weeks (+/- 3 days).

Study assessments presented in the Study Calendar (Section [3.5](#)).

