6.3 RESPONSE CRITERIA

For the purposes of this study, patients should be re-evaluated for response every 8 weeks. Response and progression will be evaluated in this study using the iRANO (Immunotherapy Response Assessment in Neuro-oncology) criteria that provides special consideration for the development of pseudo progression, given that the treatment is designed to evoke an immune/inflammatory response. The iRANO criteria provide special considerations for immunotherapy response assessment and represent an integration with established RANO criteria. The iRANO criteria are provided and fully explained in [Appendix D](#).

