- Clear clinical deterioration not attributable to other causes apart from the tumor (e.g. seizures, medication side effects, complications of therapy, cerebrovascular events, infection, etc.). The definition of clinical deterioration is left to the discretion of the investigator but it is recommended that a decline in the Karnofsky Performance Score (KPS) from 100 or 90 to 70 or less, a decline in KPS of at least 20 from 80 or less, or a decline in KPS from any baseline to 50 or less, for at least 7 days, be considered neurologic deterioration, unless attributable to co-morbid events or changes in corticosteroid dose.
- Failure to return for evaluation due to death or deteriorating condition

Classification of progressive disease may be deferred for up to three months for patients with initial radiographic findings consistent with progressive disease (criteria a and b above) as detailed below. However, if follow-up imaging after three months confirms progression or if the patient experiences significant clinical decline at any time, the date of actual progression will be back-dated to the first date that the patient met criteria for progression and such patients should discontinue further immunotherapy.

Stable Disease (SD): All of the following criteria must be met:

- Does not qualify for CR, PR, or progression.
- All measurable and non-measurable sites must be assessed using the same techniques as baseline.
- Stable clinically.

Unknown Response Status: Progressive disease has not been documented and one or more measurable or non-measurable lesions have not been assessed.

Patients who require increased corticosteroids within two weeks of MRI assessment (relative to the dose taken at the time of the prior assessment) cannot be classified as CR, PR or SD and should be classified as non-evaluable at that time point. Conversely, patients who decrease corticosteroids within two weeks of MRI assessment (relative to the dose taken at the time of the prior assessment) cannot be classified as PD and should be classified as non-evaluable.

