10.3.2 Analysis of the Secondary Endpoint(s)

The similar analyses will be performed for PFS at 12 months as those for PFS6. We will assess the relationship between the neoantigen burden in tumor prior to the treatment and the PFS using the proportional hazard model. The neoantigen burden and HMP status (HMP/NHMP) will be included in the model as the covariates, and their potential interaction will be assessed. Other important baseline prognostic factors will also be included in the model to adjust for the potential confounders. We will evaluate the relationship between the neoantigen burden in tumor prior to the treatment and the objective response using logistic regression with the neoantigen burden and HMP status as covariates. Linear mixed model will be used to examine the trajectory of the longitudinal measures of symptom burden quantified using the MDASI-Brain tumor module. Random intercept will be included to account for the within-subject correlation and HMP status will be included as a covariate.

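### Section 10.2.2 keeps out of the response set treated patients who died or could not return before any re-evaluation, although 6.3.2 classes them as progressive disease

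*Combined protocol and SAP*

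**What the plan says.** Section 10.2.2 sets three conditions for the response set: measurable disease at baseline, and patients who "have received at least one cycle of therapy, and have had their disease re-evaluated will be considered evaluable for response". A Note adds one exception: "Patients who exhibit objective disease progression prior to the end of cycle 1 will also be considered evaluable".

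Section 6.3.2.1 lists the PD criteria, any one of which is enough. Two of them need no scan: "Clear clinical deterioration not attributable to other causes apart from the tumor" and "Failure to return for evaluation due to death or deteriorating condition". The same section has a separate Unknown Response Status for patients with unassessed lesions and no documented progression.

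On timing, 3.1 sets a cycle at 4 weeks and 6.3 states that "patients should be re-evaluated for response every 8 weeks". Footnote 7 to the calendar in 3.5 puts the first on-treatment MRI at week 8, give or take 7 days. The calendar also has physical and neurological examination and KPS on day 1 of each cycle.

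The relation between neoantigen burden and treatment response is a secondary objective (1.1.2). Section 10.3.2 analyses it with a proportional hazards model for PFS and with a model for "the objective response using logistic regression with the neoantigen burden and HMP status as covariates". Neither model names its analysis population. For patients with measurable disease, 10.2.2 is the only response set defined.

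**The concern.** The two sections treat the same patient differently. One says the outcome is known and is progression; the other says the patient cannot be evaluated. The patients affected are those who do worst earliest, so they are left out because of what happened to them.

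Two things are at stake. Any response rate quoted from this set uses a denominator from which some failures have been removed. The logistic regression for the secondary neoantigen objective also loses clear non-responders, from a trial of at most 59 patients (29 HMP, 30 NHMP). The exploratory response correlations in 10.3.5 name no population either and could inherit the same set.

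**Working it through.** **Step 1: apply both sections to the same patient.** All rows assume measurable disease at baseline and at least one infusion.

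| Course before the first re-evaluation | Under 6.3.2.1 | Under 10.2.2 |
|---|---|---|
| Objective progression before the end of cycle 1 | PD | Evaluable, by the Note |
| Death or deterioration in cycle 1 preventing return, no objective progression shown | PD | Not evaluable: no full cycle, no re-evaluation, Note not clearly met |
| Death or deterioration preventing return after cycle 1, before any re-evaluation | PD | Not evaluable: no re-evaluation, Note expired at about week 4 |
| Deterioration seen at a clinic visit, no scan | PD | Unclear: the visit may count as re-evaluation |
| No assessment for another reason, no documented PD | Unknown Response Status | Not evaluable; no conflict |

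The second and third rows are the contradiction.

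**Step 2: direction for the response rate.** CR and PR in 6.3.2.1 need measured shrinkage sustained for at least 4 weeks. A patient never re-evaluated cannot meet either. With R responders among N treated patients with measurable disease, and k such patients dropped, the evaluable-only rate is R/(N−k) and the full rate is R/N. Their ratio is N/(N−k), which is never below 1.

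**Step 3: size.** The plan sets no target, sample size or power for response, so there is no planned figure to reproduce. The documents do not give k, so I assume 5% to 20% of N, rounded to whole patients. I also take N at its maximum; 2.1.1 does not require measurable disease, so N may be smaller.

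- HMP, N = 29: k = 1 gives 29/28 = 1.036; k = 6 gives 29/23 = 1.261.
- NHMP, N = 30: k = 2 gives 30/28 = 1.071; k = 6 gives 30/24 = 1.250.

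The relative overstatement is therefore about 4% to 26%. In absolute terms, assuming 3 responders:

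- HMP: 3/29 = 10.3%, against 3/26 = 11.5% with 3 dropped and 3/24 = 12.5% with 5 dropped.
- NHMP: 3/30 = 10.0%, against 3/27 = 11.1% with 3 dropped and 3/25 = 12.0% with 5 dropped.

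**Step 4: the documents' own illustration.** Section 1.2.4 reports a randomised glioblastoma trial with 182 patients on nivolumab, 153 of them evaluable, and a response rate of 8%. Then 0.08 × 153 = 12.2, or about 12 responders, and 12/153 = 7.8% reproduces the 8%. Over all treated patients it is 12/182 = 6.6%. The non-evaluable share is 29/182 = 15.9%, and the ratio is 182/153 = 1.19. The reasons for non-evaluability are not given.

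**Step 5: is the window one in which failures occur?** Assume exponential PFS and take 6 months as 26 weeks, so that PFS at week t is PFS6^(t/26). For PFS6 from 0.386 down to 0.10, between 25% and 51% of patients progress by week 8, and 12% to 21% of all patients do so between weeks 4 and 8. Only those never re-evaluated would be dropped. That share is not given, so these figures do not estimate k.

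**Step 6: the neoantigen odds ratio.** If the dropped non-responders resemble the retained ones in neoantigen burden and HMP status, the odds ratio is unbiased and only the intercept and the precision change. If their burden is lower, a positive association is weakened; if it is higher, the association is exaggerated. The documents do not say which holds.

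**The case against.** The best defence is that the gap is narrow. Section 10.2.2 asks for re-evaluation, not for a scan, and the calendar provides an examination and KPS at each cycle. A reader might infer that every patient who declines before week 8 is excluded. The text does not support that, because decline seen at a visit may count as re-evaluation. Death or failure to return cannot be read that way, so this limits the gap without closing it.

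It is also fair that response rate is not a listed objective and that 10.3 plans no estimate of it. A reader might infer that early failures leave the neoantigen analysis altogether, or that the primary result is affected. Neither follows: the hazards model for PFS and primary PFS6 are not tied to 10.2.2.

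A reader might further infer that the neoantigen association is pulled towards zero. That needs early failures to have lower burden. The rationale in 10.1.1 likens HMP tumours to recurrent glioblastoma, which across the trial would point the other way. HMP status is already a covariate, and the direction within a cohort is unknown.

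Nor can the 16% from the cited trial be carried over to 59 patients. Some of its non-evaluable patients may have lacked measurable disease, and 10.1.1.1 counts the 59 as patients with at least one cycle, so losses within cycle 1 are not among them.

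What remains is the contradiction itself and the certain direction of its effect on a response rate.

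**Conclusion.** The concern holds in a limited form. As written, 10.2.2 excludes from the response set treated patients with measurable disease whom 6.3.2.1 classes as PD because they died or deteriorated and were never re-evaluated, unless objective progression was shown in cycle 1. Any response rate from that set is at or above the rate in all treated patients with measurable disease, and the logistic regression loses these non-responders if it uses the set.

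The direction for the response rate follows from the definitions alone. The size does not: 4% to 26% relative rests on an assumed 5% to 20% dropped, and the 8% against 6.6% in the cited trial is illustrative only. Neither the size nor the direction of any bias in the neoantigen odds ratio can be determined from the documents. This is worth correcting, but it does not threaten the primary endpoint.

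**What to change.** Reconcile 10.2.2 with 6.3.2.1 as follows.

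- Define the response set as all patients with measurable disease at baseline who receive any nivolumab.
- Count every patient who meets a PD criterion in 6.3.2.1 as an evaluable non-responder. This includes death, or failure to return because of deterioration, without a scan.
- Keep Unknown Response Status for patients unassessed for other reasons, and count them in the denominator as not having responded.
- Name this set in 10.3.2 for the logistic regression on objective response, with the evaluable-only set as a sensitivity analysis.
- Leave the MDASI-BT comparison of responders and non-responders (10.3.2.1) in its stated intention-to-treat population, using the same 6.3.2.1 classification. Moving it to the measurable-disease set would remove patients whom that analysis now includes.

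The cost is wording only: no added patients, visits or data. Any reported response rate will be slightly lower.

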⁷ MRI of brain with gadolinium at screening/baseline and every 8 (+/- 7 days) weeks after beginning of treatment and at 60 (+/- 14 days) day follow up visit after last dose of Nivolumab. Note: if treatment was discontinued because of progression, the 60 days imaging is not necessary. Subjects taken off treatment before completion of 1 year of treatment and without PD at the 28-Day Safety Follow-up visit will be followed till disease progression (MRI scans every 8 (+/- 7 days) weeks with the first assessment 8 weeks after the previous tumor assessment) or 1 year after start of treatment whatever comes first.

⁸ Blood samples will be drawn prior to the initiation of treatment of cycle 1, 2, 3, 5, 7, 9, 11, 13, 15 or until disease progression, whatever comes first. Blood samples will be collected at treatment discontinuation and if patient undergoes surgical procedure after treatment discontinuation, blood samples will be collected for analysis. Also, at the 60 (+/- 14 days) day follow up visit.

⁹ At baseline and then within 7 days prior to each imaging study. After disconnection of treatment should be completed every 6 months. MDASI-BT may be completed electronically. MDASI completed within 14 days prior to treatment will be considered baseline.

¹⁰ Follow up visits are planned to be performed at 60 (+/- 14 days) and 100 (+/- 14 days) days after the last dose of Nivolumab to evaluate patient's safety. After this visit, subjects will be followed every 6 months (\pm 1 month) for survival by phone call or e-mail. Note: Subjects taken off treatment before completion of 1 year of treatment and without PD at the 28-Day Safety Follow-up, will be invited for MRI evaluations every 8 (+/- 7 days) weeks until PD or 1 year after start of treatment whatever comes first.

¹¹ If subjects are unable or not willing to come to NIH for follow up visits, they will be followed by phone call or e-mail for AEs and survival.

¹² Weight needs to be recorded once per cycle of infusion.

Abbreviated Title: Ph II Nivo IDH-mutant Gliomas

Version Date: 03/24/2023

¹³ If patient undergoes surgical procedure after treatment discontinuation, tumor tissue will be collected for analysis. Tumor sample obtained at disease progression, if available.

¹⁴ Optional. Height may be taken at any timepoint during the study, at the discretion of the investigator.

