6.3.2 Response Criteria

6.3.2.1 Response Criteria: RANO Criteria with the iRANO update ([Appendix D](#))

Complete Response (CR): All of the following criteria must be met:

- Complete disappearance of all enhancing measurable and non-measurable disease sustained for at least 4 weeks. In the absence of a confirming scan 4 weeks later, this scan will be considered only stable disease.
- No new lesions.
- All measurable and non-measurable lesions must be assessed using the same techniques as baseline.
- Patients must be on no steroids or on physiologic replacement doses only.
- Stable or improved non-enhancing (T2/FLAIR) lesions
- Stable or improved clinically, for clinical signs and symptoms present at baseline and recorded to be disease related

Patients with residual non-measurable disease cannot have a complete response. The best response possible is stable disease.

Partial Response (PR): All of the following criteria must be met:

- Greater than or equal to 50% decrease compared to baseline in the sum of products of perpendicular diameters of all measurable enhancing lesions sustained for at least 4 weeks.

In the absence of a confirming scan 4 weeks later, this scan will be considered only stable disease.

- No progression of non-measurable disease.
- No new lesions.
- All measurable and non-measurable lesions must be assessed using the same techniques as baseline.
- The steroid dose at the time of the scan evaluation should be no greater than the dose at time of baseline scan.
- Stable or improved non-enhancing (T2/FLAIR) lesions on same or lower dose of corticosteroids compared to baseline scan.
- Stable or improved, for clinical signs and symptoms present at baseline and recorded to be disease related clinically.

Progressive Disease (PD): Any of the following criterion must be met:

- > 25% increase in sum of the products of perpendicular diameters of enhancing lesions (over best response [smallest tumor size] or baseline if no decrease) on stable or increasing doses of corticosteroids
- Any new enhancing measurable lesion that when added to the change in initial tumor(s) exceeds a 25% increase in cross-sectional area.

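### Section 10.2.2 leaves out of the objective-response set patients who die or deteriorate without a post-baseline evaluation, although 6.3.2.1 scores them as progressive disease

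*Combined protocol and SAP*

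**What the plan says.** Section 10.2.2 sets three conditions for the objective-response set: measurable disease at baseline, at least one cycle, and a re-evaluation. Patients who meet the first and "have received at least one cycle of therapy, and have had their disease re-evaluated will be considered evaluable for response". A note in the same paragraph adds one exception: "Patients who exhibit objective disease progression prior to the end of cycle 1 will also be considered evaluable".

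In Section 6.3.2.1 the list of PD criteria is headed "Any of the following criterion must be met", so one is enough. The last entry is "Failure to return for evaluation due to death or deteriorating condition", which by its nature applies to patients with no further evaluation.

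On timing, Section 3.1 sets a cycle at 4 weeks, give or take 3 days. The study calendar (3.5) places MRI "every 8 (+/- 7 days) weeks after beginning of treatment", and Section 6.3 says that "patients should be re-evaluated for response every 8 weeks".

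Response enters a secondary objective (1.1.2) through its relation to neoantigen burden. Section 10.3.2 models "the objective response using logistic regression with the neoantigen burden and HMP status as covariates" and names no analysis set for that model.

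**The concern.** The two sections disagree about the same patients. One gives them a definite outcome, PD, which is a non-response. The other takes them out of the set in which response is counted, because nobody re-evaluated them. The note does not close the gap. It covers only progression that is objective and only the first cycle, while the first scheduled scan falls about four weeks after that cycle ends.

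The loss is not neutral. A responder must have had a scan, so this route never removes one. Any response rate on the 10.2.2 set is pushed upward, and a regression of response on that set may be distorted if the loss is related to its covariates.

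**Working it through.** The plan states no response rate, power or sample size for objective response, so there is no figure of its own to reproduce. The check has three parts.

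**1. The two sections side by side.** All four patients are treated and have measurable baseline disease.

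| Patient | 6.3.2.1 | 10.2.2 |
|---|---|---|
| Completes cycle 1, dies at week 6, no scan | PD | Outside: not re-evaluated; note covers cycle 1 only |
| Dies or deteriorates at week 3, no objective progression, does not return | PD | Outside: fails the cycle and re-evaluation conditions; note needs objective progression |
| Unscheduled MRI at week 3 shows progression | PD | Inside, through the note |
| Completes cycle 1, clinical decline recorded at a visit in week 6, no MRI | PD | Depends on what re-evaluated means |

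The gap is therefore death or deterioration without a post-baseline evaluation, either in cycle 1 without objective progression or between about week 4 and the week-8 scan.

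**2. Effect on a response rate.** With R responders among N treated patients and k non-responders lost, the set gives R/(N − k) where the full count gives R/N. The ratio is N/(N − k). I take N = 59 (29 HMP plus 30 NHMP, Section 10.1.1.1) and treat all as having measurable disease. The documents do not give k; I assume 3 to 12 (about 5% to 20%).

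| R | Full count | k = 3 | k = 12 |
|---|---|---|---|
| 5 | 5/59 = 8.5% | 5/56 = 8.9% | 5/47 = 10.6% |
| 12 | 12/59 = 20.3% | 12/56 = 21.4% | 12/47 = 25.5% |

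The relative inflation runs from 59/56 = 1.05 to 59/47 = 1.26.

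**3. Effect on the logistic model, if it uses this set.** Let d be the proportion of non-responders lost. Responders are never lost, so

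logit P(response | included) = logit P(response) − ln(1 − d).

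- *Loss differs by cohort only.* The added term takes one value per cohort and is absorbed by the intercept and the HMP coefficient. The spurious HMP odds ratio is (1 − d_NHMP)/(1 − d_HMP). With assumed d_NHMP = 10%, it is 0.9/0.8 = 1.13, 0.9/0.7 = 1.29 or 0.9/0.6 = 1.50 for d_HMP of 20%, 30% or 40%. The neoantigen coefficient does not change.
- *Loss depends on burden.* Take an assumed unadjusted table with 6/29 responders at high burden and 2/30 at low burden: (6/23)/(2/28) = 3.65. Drop 9 non-responders. If all are low-burden, (6/23)/(2/19) = 2.48. If split evenly, (6/18.5)/(2/23.5) = 3.81. If all are high-burden, (6/14)/(2/28) = 6.00. The odds ratio can move either way.

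**The case against.** The strongest reply is that the target is small. No response-rate objective appears in Section 1.1, and 10.3 plans no estimate of one. Section 10.3.2 names no set for the logistic model, so applying 10.2.2 there is the natural reading but still an inference. The word re-evaluated is undefined. Section 3.5 schedules physical and neurological examination and performance status on day 1 of each cycle, so a recorded clinical decline might qualify. All of this stands, and it limits the point. It does not rescue the patient who dies unscanned at week 6.

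Four stronger readings are tempting, and the documents do not support them.

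- *The bias favours the idea that high burden responds better.* The rationale in 10.1.1 likens HMP tumours to recurrent glioblastoma and NHMP tumours to recurrent anaplastic astrocytoma, which suggests more early failure in HMP. But HMP status is already a covariate in the logistic model, so loss that differs only by cohort leaves the neoantigen coefficient alone. Section 1.2.7 also reports that 8 of the first 15 NHMP patients had glioblastoma, which weakens the assumed contrast.
- *The cited recurrent-glioblastoma trial measures the loss.* Section 1.2.4 gives 182 patients who received nivolumab, 153 evaluable and 8% responding. That leaves out 29/182 = 16%, and 0.08 × 153 = 12.2 responders would be 6.7% of 182. No reason is given for the 29. Some may have lacked measurable disease, and such patients would stay out under any fix proposed here.
- *Early progression measures the loss.* If PFS is exponential, the share failing in weeks 4 to 8 is 2^(−4/m) − 2^(−8/m). This is 19% for a median m of 9 weeks and 16% for 13 weeks (benchmarks in 10.1.1), and 23% for the 1.5 months in 1.2.4. These figures count progression. A patient whose progression is seen on a scan has been re-evaluated and stays in; only those who never return are lost.
- *The primary endpoint is affected.* Section 10.2.2 defines a set for objective response. It does not govern PFS6, overall survival or the proportional hazards model of neoantigen burden on PFS.

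A distortion in the HMP coefficient would also be small beside its sampling error. At 8% response in 29 and 30 patients, the standard error of the log odds ratio is √(1/2.32 + 1/26.68 + 1/2.40 + 1/27.60) = 0.96, against ln 1.29 = 0.25.

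**Conclusion.** The conflict between 10.2.2 and 6.3.2.1 is in the text and should be resolved. For patients lost by this route the direction of bias in a response rate is certain: upward. Its size is unknown because the documents do not say how many patients would fail to return. The 1.05-fold to 1.26-fold range rests on the assumed loss of 3 to 12 out of 59.

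The regression effect is conditional twice: on the model using this set, and on how the loss is distributed. Differential loss by cohort reaches the HMP coefficient. The neoantigen coefficient, which serves the secondary objective, is at risk only if loss depends on burden within cohort, and the documents give no basis for saying which way it would move.

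**What to change.** Amend 10.2.2 along these lines: all treated patients with measurable disease at baseline who meet any PD criterion in 6.3.2.1, including failure to return because of death or deterioration, are in the response set as non-responders, whether or not they completed cycle 1 or had a scan.

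- Name this set for any response summary and for the logistic regression in 10.3.2.
- Report the re-evaluated-only subset as a sensitivity analysis.
- Show patients who stop for other reasons before any scan separately as unknown response, a category that 6.3.2.1 already has. Counting them all as non-responders would go further than reconciling the two sections requires.
- Say whether a clinic examination without MRI counts as a re-evaluation.
- Make the matching change in 10.2.3, which has the same cycle and re-evaluation conditions.

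The cost is a few sentences and no new data. The reported response rate becomes slightly lower.
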